1. INTRODUCTION AND BACKGROUND

[figure not shown]
1.1. Introduction

Etigilimab, a humanized immunoglobulin G (IgG1) monoclonal antibody that specifically binds to human TIGIT (T-cell immunoreceptor with Ig and ITIM domains), blocks TIGIT interaction with its ligand PVR (poliovirus receptor), inhibits downstream signaling, and mediates target cell killing. Anti-TIGIT was shown preclinically to inhibit tumor growth in mouse models. Etigilimab is being developed for the treatment of solid cancer tumors in humans.

1.2. Background

TIGIT is an important co-inhibitory receptor; it contains 2 immunoreceptor tyrosine-based inhibition motifs (ITIMs) and its expression at the surface of immune cells is markedly increased upon activation. TIGIT is found on CD4 and CD8 T-cells, on natural killer (NK) cells, and on a subset of Tregs (regulatory T cells) (Chan et al 2012, Yu et al 2009, Joller et al 2014). Consistent with its structure and expression pattern, TIGIT was found to have an inhibitory function on both T-cells and NK cells and to increase Tregs' suppressive capacity (Joller et al 2014, Joller et al 2011, Levin et al 2011, Stanietsky et al 2009). Known ligands for TIGIT are PVR, PVRL2, and with weaker binding, PVRL3 and PVRL4 (Yu et al 2009) (data on file at Mereo). The TIGIT signaling axis also contains a co-stimulatory receptor, CD226, which binds to PVR and PVRL2 with lower affinity than TIGIT (Bottino et al 2003, Martinet & Smyth 2015). Therefore, when TIGIT is expressed, the ligands preferentially engage TIGIT rather than CD226, leading to immune suppression.

Given TIGIT's immunomodulatory functions and the expression of PVR and PVRL2 in most cancers (Stanietsky et al 2009, Gromeier et al 2000), it has been postulated that blocking TIGIT binding to its ligands may reverse tumor-induced immune suppression and result in tumor regression in a broad range of cancer types (Figure 1).

Figure 1 Broad Expression of TIGIT's Ligand PVR across TCGA Tumor Collection

Abbreviations: PVR = poliovirus receptor; TCGA = The Cancer Genome Atlas; RPKM = reads per kilobase per million; TIGIT = T-cell immunoreceptor with Ig and ITIM domains

Legend: PVR gene expression levels are plotted for 32 different tumor types as available from The Cancer Genome Atlas (TCGA). Each symbol represents one patient. Levels are expressed in reads per kilobase per million (RPKM).

The anti-tumor activity of TIGIT blockade was verified in different murine cancer models where it was shown to operate through multiple mechanisms to inhibit tumor growth (Johnston et al 2014, Kurtulus et al 2015). Further supporting TIGIT targeting for cancer treatment are reports of its overexpression on patient tumor-associated T-cells (Johnston et al 2014, Chauvin et al 2015).

TIGIT targeting is likely to be most efficient when combined with other immunotherapies. In preclinical and clinical studies, targeting TIGIT together with the programmed death-1/programmed death ligand-1 (PD-1/PD-L1) pathway demonstrated superior tumor suppression compared to either monotherapy.

A Phase 1a/b open-label, dose-escalation study was conducted to evaluate the safety and pharmacokinetics (PK) of etigilimab administered as a single agent or in combination with nivolumab to subjects with locally advanced or metastatic solid tumors (study number 313M32-001). A total of 23 subjects were enrolled on the Phase 1a portion of the study for treatment with etigilimab and 10 subjects were enrolled on the Phase 1b portion of the study for

treatment with etigilimab in combination with nivolumab. Doses investigated in the Phase 1a portion of the study were [REDACTED] mg/kg (for dose-escalation) and [REDACTED] mg/kg (for dose-expansion), and doses evaluated in the Phase 1b dose-escalation portion of the study were [REDACTED] mg/kg. To characterize the PK properties of etigilimab and pharmacodynamic responses to treatment, blood samples were taken at various timepoints before and after dosing. Subjects underwent tumor assessments at screening and every 8 weeks during the study. Subjects remained on treatment at the discretion of the investigator until disease progression, unacceptable toxicity, initiation of a new anticancer therapy, withdrawal of subject consent, physician decision, or death. Efficacy endpoints included tumor response. Time-to-event endpoints included duration of response (DoR), progression-free survival (PFS), and overall survival. Safety endpoints included adverse events (AEs), vital signs, 12-lead electrocardiograms (ECGs), clinical laboratory testing, and immunogenicity testing.

Treatment with etigilimab was well-tolerated in study 313M32-001; no dose-limiting toxicities (DLTs) were reported in either the Phase 1a or Phase 1b portions of the study. Thus, the maximum tolerated dose was not reached. All subjects in the study reported 1 or more treatment-emergent AEs (TEAEs). The most commonly reported TEAEs in the Phase 1a portion of the study were nausea (8 subjects, 34.8%) and fatigue (7 subjects, 30.4%), and the most commonly reported TEAEs in the Phase 1b portion of the study were decreased appetite and nausea (each reported by 5 subjects, 50.0%). Immune-related TEAEs were reported by 10 subjects (43.5%) in the Phase 1a and 5 subjects (50.0%) in the Phase 1b portions of the study. The most commonly reported immune-related TEAEs in the Phase 1a portion of the study were pruritus, rash, and maculopapular rash (each reported by 3 subjects, 15.0%). In the Phase 1b portion of the study, the most commonly reported immune-related TEAEs were pruritus, rash, and pruritic rash (each reported by 2 subjects, 20.0%). The most commonly reported National Cancer Institute Common Terminology Criteria for Adverse Events (NCI CTCAE) Grade 3 or higher abnormal laboratory test results in the Phase 1a portion of the study were lymphocytes (8 subjects 34.8%), alkaline phosphatase (3 subjects 13.0%), and alanine aminotransferase (ALT) and sodium (each reported by 2 subjects, 8.7%). In the Phase 1b portion of the study, the most commonly reported CTCAE Grade 3 or higher laboratory results were alkaline phosphatase (3 subjects, 30.0%) and aspartate aminotransferase (AST) (2 subjects, 20.0%). Treatment-emergent AEs with a fatal outcome were reported for 3 subjects (13.0%) in the Phase 1a portion of the study and 2 subjects (20.0%) in the Phase 1b portion of the study. There were no related TEAEs with a fatal outcome in the Phase 1a and the Phase 1b portions of the study.

In the single agent portion of the study no Response Evaluation Criteria in Solid Tumors (RECIST) responses were reported. However, a number of subjects demonstrated tumor reduction or stable disease (SD). The tumor types where clinical benefit was observed included endometrial, fallopian tube, parotid adenocarcinoma, salivary duct adenocarcinoma, and colorectal cancer. In the group who received both etigilimab and nivolumab, all subjects treated received a prior checkpoint point inhibitor. A partial response was observed in a patient with ovarian cancer, and other patients with microsatellite instability (MSI), colorectal (CRC), head and neck, gastric and renal cancer appeared to benefit with evidence of tumor reduction or stabilization.

The median (95% confidence interval [CI]) PFS in the Phase 1a portion of the study was 56.0 (51.0, 112.0) days, and the PFS estimates (95% CI) at 3, 6, and 12 months were 30.0%

(12.3, 50.1), 10.0% (1.7, 27.2), and 0%, respectively. The median (95% CI) PFS in the Phase 1b portion of the study was 57.5 (14.0, 224.0) days, and the PFS estimates (95% CI) at 3, 6, and 12 months were 37.5% (8.7, 67.4), 25.0% (3.7, 55.8), and 0%, respectively. The median (95% CI) overall survival in the Phase 1a portion of the study was 173.0 (88.0, 268.0) days, and the survival estimates (95% CI) at 3, 6, and 12 months were 30.0% (12.3, 50.1), 10.0% (1.7, 27.2), and 0%, respectively. The median (95% CI) overall survival in the Phase 1b portion of the study was 205.0 (19.0, N/A) days, and the survival estimates (95% CI) at 3 months were 57.9% (15.3, 85.2) and not applicable at 6 and 12 months.

1.3. Study Design

This is an open-label, multicenter, Phase 1b/2 basket study designed to evaluate the efficacy, safety, tolerability, pharmacokinetics (PK), and pharmacodynamics (PD) of etigilimab in combination with nivolumab in subjects with recurrent, locally advanced and/or metastatic solid tumors who are not candidates for available, curative standard of care therapies. In cohorts enrolling tumor types for whom anti-PD-1 antibody therapy is approved treatment for recurrent, locally advanced or metastatic disease, subjects may be enrolled prior to treatment with anti-PD-1 antibody therapy.

Subjects will be assigned to receive etigilimab (█ mg every 2 weeks for subjects \geq 50 kg, █ mg/kg dose every 2 weeks for subjects <50 kg) in combination with nivolumab (240 mg every 2 weeks) and will continue until protocol-defined discontinuation criteria are met (refer to [Section 7](#)). Additional doses and schedules may also be evaluated. This study will evaluate both subjects who have not previously been treated with immune checkpoint inhibitors (CPI) as well as those who have received prior CPI therapy and will include tumor types chosen for higher prevalence of TIGIT, and in select cohorts, subjects with high PD-L1 expressing tumors as measured by immunohistochemistry (IHC). Tumor types selected for this study include recurrent, locally advanced and/or metastatic endometrial carcinoma (EC), cervical cancer (CC), gastric cancer and gastro-esophageal junction carcinoma (GC), squamous cell carcinoma of the head and neck (HNSCC), ovarian cancer (OC), rare cancers (metastatic testicular germ cell tumor, uveal melanoma and sarcoma) and any subject with concomitant tumor mutation burden high (TMB-high) and microsatellite stable (MSS) tumors. As TIGIT has been implicated in PD-L1 resistance, subjects who have received or progressed following a CPI (post-CPI subjects) will also be enrolled in select tumors including EC, HNSCC and TMB-high/MSS tumors. Parallel cohorts of up to 20 subjects per cohort will be evaluated.

[figure not shown]
Cohorts will be enrolled at the discretion of the sponsor. Selected cohorts will be open for the first 20 subjects enrolled without increasing the total number of subjects proposed for the trial. During the conduct of this open-label study an Independent Data Monitoring Committee (IDMC) will be established and will review study data on an ongoing basis. The IDMC will consist of at least 3 members with expertise in their field of practice as well as in the conduct of clinical studies. The committee members will be free of significant conflicts of interest. The IDMC will hold regularly scheduled data review meetings at pre-specified intervals as defined in the IDMC charter. The IDMC will also be available on an ad hoc basis e.g., to provide guidance related to any emerging safety signals or if requested by the sponsor.

The IDMC will have periodic safety reviews of the study that will start after the first 20 subjects are enrolled. A safety review of the study will be conducted by the IDMC approximately every 3 months. The IDMC and sponsor may decide to meet less frequently, based upon rate of accrual and the amount of new data generated (refer to the IDMC charter).

Futility monitoring will be evaluated in each cohort of the study using a Simon's two-stage design as described in [Section 9.1](#) of the protocol. For each cohort, the second stage may be opened for enrollment only after discussion with the IDMC and the sponsor. The sponsor may have an independent assessment of responses to verify investigator-reported responses. The responses based on independent assessments, if available, will be used for sensitivity analysis with sponsor and will make recommendations regarding study conduct, including whether to continue, modify, or stop the study.

An analysis will be conducted when the first 30 TIGIT IHC biopsy results have been complete. This is to confirm the expected TIGIT positive rate based on data on file and reported in the literature. The efficacy of the combination will be evaluated by cohort and efficacy of the combination will be evaluated based on TIGIT IHC positive subjects.

Figure 2 Study Schema

Abbreviations: ECOG = Eastern Cooperative Oncology Group; GEJ = gastroesophageal junction adenocarcinoma; Tumor mutation burden – high (TMB-H) + microsatellite stable (MSS); OS = overall survival; PD = pharmacodynamic; PD-1 = programmed death-1; PD-L1 = programmed death ligand-1; PFS = progression-free survival; PK = pharmacokinetic; ADA=anti-drug antibody

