9.1. Sample Size Determination

This is a Phase 1b/2 open-label basket study of etigilimab (MPH313) (█ mg dose for subjects \geq 50 kg, █ mg/kg dose for subjects $<$ 50 kg) IV administered Q2W with nivolumab 240 mg Q2W to evaluate preliminary anti-tumor activity, safety and tolerability, PK parameters, immunogenicity, and biomarkers in up to 9 cohorts of subjects with endometrial carcinoma, HNSCC, cervical cancer, ovarian cancer, gastric cancer and gastroesophageal junction adenocarcinoma, TMB-H/MSS cancer, sarcoma, germ cell tumors, and uveal melanoma. Each cohort will be evaluated using a Simon Two-Stage design appropriate to the clinically meaningful response rate for the indication as depicted in [Figure 5](#) below. Interim futility monitoring for each individual cohort using the clinically meaningful response rate criteria per cohort will be carried out in accordance with the optimal Simon Two-Stage design when up to 10 subjects have sufficient data (either discontinued study drug treatment or having at least one post-baseline imaging assessment) for ORR and DoR evaluation by RECIST v1.1. For each cohort, the second stage may be opened for enrollment only after discussion with the IDMC and the sponsor. The sponsor may have an independent assessment of responses to verify investigator-reported responses. The responses based on independent assessments, if available, will be used for sensitivity analysis with sponsor and will make recommendations regarding study conduct, including whether to continue, modify, or stop the study.

Figure 5 **Simon Two-stage Study Design**

Abbreviations: CC = cervical cancer; EC = endometrial cancer; GC = gastric cancer and gastroesophageal junction adenocarcinoma; GCT = germ cell tumors; HNSCC = head and neck squamous cell carcinoma; OC = ovarian cancer; SR = sarcoma; TMB-H = tumor mutational burden-high; UM = uveal melanoma

Type 1 Cohort

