The null hypothesis that the true response rate is 0.05 will be tested against a one-sided alternative that the true response rate is at least 0.2. In the first stage, 10 subjects will be enrolled and enrollment in this cohort will be halted until the response data are mature. If there are fewer than 1 responder in these 10 subjects, further enrollment in the cohort may be stopped after review of efficacy and safety data, and discussion by Sponsor with the IDMC. Otherwise, once 1 or more responders in stage 1 are observed, 19 additional subjects may be enrolled for a total of 29. The null hypothesis will be rejected and the treatment will be declared effective and worthy of further testing if 4 or more responders are observed in 29 subjects. This design yields a type I error rate of 0.0468 and power of 80.11% when the true response rate is 0.2.

Type 2 Cohort

The null hypothesis that the true response rate is 0.1 will be tested against a one-sided alternative that the true response rate is at least 0.3. In the first stage, 10 subjects will be enrolled and enrollment in this cohort will be halted until the response data are mature. If there are fewer than 2 responders in these 10 subjects, enrollment in the cohort may be stopped after review of efficacy and safety data, and discussion by Sponsor with the IDMC. Otherwise, once 2 or more responders in stage 1 are observed, 19 additional subjects may be enrolled for a total of 29. The null hypothesis will be rejected and the treatment will be declared effective and worthy of further testing if 6 or more responders are observed in 29 subjects. This design yields a type I error rate of 0.0471 and power of 80.51% when the true response rate is 0.3.

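### The design sections cap each cohort at 20 subjects, but the two-stage design, its success cut-offs and its roughly 80% power hold only at 29

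*Protocol*

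**What the plan says.** **The cap.** Protocol 1.3 states "Parallel cohorts of up to 20 subjects per cohort will be evaluated", and SAP 6.1 repeats the sentence. The synopsis in Appendix 9 does not contain it.

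**The design.** Section 1.3 also says "Futility monitoring will be evaluated in each cohort of the study using a Simon's two-stage design as described in" Section 9.1. There, "Each cohort will be evaluated using a Simon Two-Stage design appropriate to the clinically meaningful response rate for the indication". Stage 1 has 10 subjects for both cohort types. If the stage 1 threshold is met (1 responder for Type 1, 2 for Type 2), "19 additional subjects may be enrolled for a total of 29". Success is declared "if 4 or more responders are observed in 29 subjects" (Type 1) or "if 6 or more responders are observed in 29 subjects" (Type 2). For Type 1, "This design yields a type I error rate of 0.0468 and power of 80.11% when the true response rate is 0.2". For Type 2, "This design yields a type I error rate of 0.0471 and power of 80.51% when the true response rate is 0.3". The synopsis and SAP 8 carry the same numbers.

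**Related counts.**
- The sarcoma part of Cohort F (Protocol 3.1) has histology quotas of 10, 10 and 5.
- Protocol 2.1 plans 125 enrolled subjects in total.
- Protocol 2.1 has selected cohorts open for the first 10 subjects enrolled. Protocol 1.3, the synopsis and SAP 6.1 say the first 20.

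No section gives a success cut-off, type I error or power for 20 subjects, or says that a cohort passing stage 1 may exceed 20.

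**The concern.** A cohort limited to 20 has room for 10 subjects after stage 1, but the second stage needs 19. The two statements cannot both govern the same cohort, and Section 1.3 contains the cap and the cross-reference to the design that exceeds it. Making stage 2 optional, after discussion with the IDMC, does not make it fit.

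The question was live for real cohorts. SAP 6.3 records that the cervical and uveal cohorts were evaluated at the interim and approved to proceed, and the documents give two different maxima for what came next. SAP 11, which lists changes from the protocol analysis, does not mention it.

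What is at stake is how the results are described. SAP 8 states a rule for declaring the treatment effective, and roughly 80% power, without limiting either to cohorts that complete 29. A study report could carry them over to a cohort that stopped short.

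**Working it through.** **Inputs** (Protocol 9.1; SAP 8 is identical). Stage 1 n₁ = 10. Type 1: p₀ = 0.05, p₁ = 0.20, continue if r₁ ≥ 1, success if total r ≥ 4. Type 2: p₀ = 0.10, p₁ = 0.30, continue if r₁ ≥ 2, success if total r ≥ 6.

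**Formula.** For a final total N and true response rate p,

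P(success) = Σ over x ≥ r₁ of P(Bin(10, p) = x) × P(Bin(N − 10, p) ≥ r − x).

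Setting p = p₀ gives type I error; p = p₁ gives power. Terms with x ≥ r are already successes at stage 1 and are pooled as the last number in each sum below.

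**Step 1: reproduce the plan at N = 29 (stage 2 of 19).**

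- Type 1 error: 0.0210 + 0.0183 + 0.0065 + 0.0010 = 0.0468.
- Type 1 power: 0.2048 + 0.2770 + 0.1984 + 0.1209 = 0.8011.
- Type 2 error: 0.0223 + 0.0169 + 0.0065 + 0.0013 + 0.0001 = 0.0471.
- Type 2 power: 0.2024 + 0.2545 + 0.1980 + 0.1028 + 0.0473 = 0.8051 (unrounded terms).

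All four match the stated values.

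**Step 2: same stage 1 and cut-offs, stopped at N = 20 (10 further subjects).**

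- Type 1 power: 0.0865 + 0.1885 + 0.1797 + 0.1209 = 0.5756.
- Type 2 power: 0.0818 + 0.1647 + 0.1702 + 0.1000 + 0.0473 = 0.5641 (unrounded terms).

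| | Error at 29 | Error at 20 | Power at 29 | Power at 20 | Loss of power |
|---|---|---|---|---|---|
| Type 1 (≥4) | 0.0468 | 0.0153 | 80.1% | 57.6% | 22.5 points |
| Type 2 (≥6) | 0.0471 | 0.0106 | 80.5% | 56.4% | 24.1 points |

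**Step 3: could 20 be the intended size with other cut-offs?** With the stated stage 1, no cut-off at 20 gives both error ≤ 0.05 and power ≥ 80%.

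- Type 1: ≥3 gives 0.0686 and 75.9%; ≥4 gives 0.0153 and 57.6%.
- Type 2: ≥4 gives 0.1013 and 80.8%; ≥5 gives 0.0376 and 71.6%.

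Lower cut-offs have larger error and higher ones have less power. With the stated stage 1, 29 is the smallest total that meets both limits; at 28 the best power with error ≤ 0.05 is 78.6% (Type 1) and 79.3% (Type 2). So 20 is not an alternative size for the same design.

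**Step 4: other counts.**

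- Sarcoma quotas: 10 + 10 + 5 = 25, above 20 and below 29.
- Total enrolment: 4 × 29 = 116 fits within 125; 5 × 29 = 145 does not. Nine cohorts would need 9 × 29 = 261, or 9 × 20 = 180 even at the cap.

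**The case against.** The strongest answer is that nothing analysed depends on the wrong number. The total of 29 is consistent across Protocol 9.1, the synopsis and SAP 8, and Section 1.3 defers to 9.1, so the 20 looks like an uncorrected sentence. SAP 10.1.3 plans no hypothesis testing, SAP 10.8.1.1 reports ORR with a Clopper-Pearson interval, and the response table shell has no success declaration. SAP 6.3 records that the study was terminated. No estimate, interval or table would change. All of this stands and limits the severity, but it does not remove the contradiction or the unqualified power statement in SAP 8.

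Three stronger readings are tempting, and the documents do not support them.

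- *A cohort of 20 cannot use the success rule.* Responder counts only rise as subjects are added. Four (or six) responders by subject 20 already guarantee the cut-off at 29. Stopping at 20 loses late successes and cannot create false ones, which is why type I error falls.
- *The sample-size calculation is wrong.* It reproduces exactly at 29.
- *The trial was run at 56 to 58% power.* No section applies the cut-offs at 20, and the documents do not give the cohort sizes reached. The figures at 20 illustrate what the cap would cost.

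The difference between first 10 and first 20 is a separate wording point. The sentence may count subjects in the trial rather than in a cohort, so it does not bear on power.

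**Conclusion.** The inconsistency is real and sits in the current text of both documents. The stated cap of 20 cannot deliver the stated design: a cohort that stopped there would have about 57.6% (Type 1) or 56.4% (Type 2) power instead of 80.1% or 80.5%, with type I error lower at 0.015 or 0.011. The sarcoma quotas, at 25, agree with neither number.

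The power figures assume the stated stage 1 rule is followed, the cut-offs stay at 4 and 6, and the cohort ends at exactly 20. That 29 is the intended size is an inference, though a well-supported one: three concordant sections, the cross-reference in 1.3 and the exact reproduction at 29. The schema and the Simon-design figure are not shown and could not be checked; both cohort types use 29 in the text, so the allocation of cohorts to types does not affect the result.

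This should be fixed, but as a matter of wording and interpretation. It does not undermine the planned descriptive analysis.

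**What to change.** 1. **Protocol 1.3 and SAP 6.1.** Replace the limit of 20 with: *up to 29 (10 in stage 1 plus 19 in stage 2, see Section 9.1)*, citing Protocol Section 9.1 in the SAP. Say that the limit applies to each cohort as counted in 9.1 (up to 9, with sarcoma, germ cell and uveal tumours counted separately), because eligibility and the SAP displays group those three under Cohort F. The list in 9.1 names endometrial carcinoma once while eligibility has Cohorts A and G, so say how those two are counted. Add that, with 125 enrolled in total, not every cohort can reach 29; at most four can.
2. **SAP 8.** Add: *The stated cut-offs, type I error and power apply only to a cohort that completes 29 subjects; for any cohort stopped earlier the ORR is descriptive and is reported with its Clopper-Pearson CI.* Record this in SAP 11.
3. **Separate minor wording.** Reconcile first 10 (Protocol 2.1) with first 20 (Protocol 1.3, synopsis, SAP 6.1) and say whether it counts subjects in the cohort or in the trial. State whether the sarcoma quotas limit that cohort to 25.

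Do not set new cut-offs for smaller totals: stage 1 decisions and termination have already happened, so they would be post hoc.

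The cost is a few sentences, with no change to the design, the total sample size or any planned output. If the protocol is no longer being amended, the SAP changes alone are enough.
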